8.3 Time to Event

The time to clinical resolution in days will be computed as the time in number of days from the start of treatment to the date of resolution or censoring.

For subjects completing the study or being prematurely withdrawn from the study without experiencing clinical resolution, the time to event will be right-censored at the date of completion/withdrawal.

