2.3. Hypothesis

The primary hypothesis to be tested is that the CRR_12 of subjects treated with 0.08% PHMB monotherapy, is superior, or worse by no more than an acceptable pre-defined 0.20 non-inferiority margin (Δ), compared to the CRR_12 of a 0.20 PHMB + 0.1% propamidine combination therapy, administered according to the Treatment and Follow-up Protocol described in Section 5.3, which is based on a consensus of currently clinical guidelines.

Secondary hypotheses are:

- That adverse events, and those relating to toxicity in particular, are less with PHMB 0.08% monotherapy compared to the comparator.
- That time to a cure is shorter in subjects receiving PHMB 0.08% monotherapy compared to the comparator.

Note: The estimated CRR_12 from the start of treatment is 67% for the conventional (0.02% PHMB + 0.1% propamidine) combination therapy (from the sponsor's observational, case series retrospective study 038/SI²⁰) (63% when assuming a prevalence of late stage diseases in 38% of subjects).

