5.3.2. Poor Response at 3 weeks or Treatment Failure

BOX VIII POOR RESPONSE at 3 weeks.

Poor response at 3 weeks from I Trial entry or XIII RESTART: patients are managed using the guidelines in IX. Criteria for this include enlarging ulcer, stromal thinning, deteriorating corneal, inflammation (infiltrate including ring abscess), intraocular inflammation (uveitis and hypopyon) and/or scleritis.

BOX IX INTRODUCE ANTI-INFLAMMATORY TREATMENT

- a. For subjects NOT using topical steroids start these WITH oral NSAIDs. The topical steroid that is permitted in the Trial is unpreserved dexamethasone (0.1% or 0.15%). The oral NSAID used in the trial is diclofenac. The frequency of the drops and the dose of oral NSAID that is used is at the discretion of the Investigator.
- b. For subjects already on unpreserved topical dexamethasone (0.1% or 0.15%) and oral diclofenac, increase the frequency of the steroid drops and dosage of oral diclofenac when possible.

This is expected to result in an improvement for most cases and they move to BOX II.1 STABLE or BOX III IMPROVEMENT.

BOX X CONTINUED DETERIORATION

Alternatively, if continued deterioration occurs, cases move to Box XVIII - TREATMENT FAILURE and EXIT Trial.

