5.3.3. Relapse

BOX XI RELAPSE WITHIN 11 MONTHS

Relapse within 11 months, after an initial response is common. Cultures for *Acanthamoeba* and other organisms (fungi, bacteria and herpes) must be repeated, deriving from a repeated corneal biopsy, if the investigator thinks this is appropriate.

- c. If the CULTURES are NEGATIVE patients this may mean that the anti-amoebic therapy is having some effect although we have no way of being certain about this (confocal and PCR don't help as these can be positive when the organisms are non-viable). These patients are managed as described in XIII below with another 19 day course of intensive therapy, with or without anti-inflammatory therapy depending on status.
- d. If CULTURES are POSITIVE patients have TREATMENT FAILURE and managed as described in XIV and XVII below.

Box XII. EXACERBATION of inflammation is presumed to be due to inflammation secondary to the immune response to non-viable Acanthamoeba and anti-inflammatory treatment can be re-started or increased at the discretion of the PI without the need for re-culture and a further course of intensive anti-amoebic therapy. IMPORTANT: if anti-amoebic treatment had been stopped restart this when anti-inflammatory treatment is re-started.

Distinguishing between XI and XII is often difficult and guidelines for this are given in II a, b above.

Box XIII. Restart with another 19 day intensive course of anti-amoebic therapy with or without topical steroids and oral NSAIDS:

- a. If patients were not on these at the time of the relapse of infection we recommend not using these until after the 19 day course of intensive treatment and depending on response move to as above.
- b. If they were on them at the time of the relapse continue at a dose determined by the PI and follow pathways II, III, IX or X.

Box XIV. CULTURE POSITIVE these patients are Exit Trial and are managed as described in XVII below.

Box XV. SCLERITIS UNRESPONSIVE to treatment in IX. This is a failure (see XVII below).

Box XVI. RELAPSE after day 335 or ingoing inflammation and treatment at day 365: this is a treatment failure and is managed as described in XVII below

Box XVII. TREATMENT FAILURE and EXIT TRIAL. The treatment randomization allocation will be opened by the Sponsor at this point. Trial drug (PHMB 0.08%) will be available to the patient, if requested by the Investigator, providing the patient continues trial follow up for safety evaluation.

XVIII. Summary of Study end points.

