7.9.1 Primary Efficacy Variable

The main endpoint disease resolution 12 months after baseline will be assessed at each visit up to study day 365.

Clinical resolution 12 months after baseline for a patient is defined as:

The percentage of subjects cured 30 days after discontinuing all study therapies, within 12 months of randomization. A clinical resolution classification requires a Yes response to the eCRF variable CRYN question: "Was clinical resolution obtained?" at one of the study visits from day 1 up to study day 365 in combination with a response *No* to the eCRF variable RELAPYN question "Did the subject experience relapse since the last visit?" at the pursuing visits, up to the last recording of this information. There should be no relapses after (the last) clinical resolution classification. Discontinued subjects will be regarded as not cured.

For patients defined as fulfilling disease resolution within 12 months, the date of the visit at which annotated CRYN is first answered with a Yes will be used as the date of resolution. The time-to-cure secondary variable will be the number of days from randomisation to the visit where resolution was recorded.

Since it is also possible to test for non-inferiority if the superiority hypothesis is not met, additional conditions are specified (see list below) to meet the strict requirements of a non-inferiority study, making it feasible to test for non-inferiority using the results from the superiority analysis, without a further separate analysis. The 90% CI for the difference between the treatments obtained from the superiority analysis gives the necessary information. Position of the lower end of the CI relative to a pre-defined agreed 0.20 non-inferiority margin (Δ) provides the key information for making decisions (conclusions) about non-inferiority.

PHMB has received the orphan drug designation. The use of 90% CI for the difference between the two treatments is to provide a 95% lower CI limit for non-inferiority.

The additional conditions specified to make testing for non-inferiority feasible are the following:

- Pre-defined non-inferiority margin (Δ =0.20) based on both clinical and statistical considerations, i.e., chosen on the basis of external information and not chosen to fit the data.
- Analysis of the FAS and the PPAS, giving similar results with respect to p-values and CIs for the
 efficacy measure at issue.

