7.9.3 Secondary Efficacy Variables¹

Time-to-cure comparison between the treatment groups is specified as efficacy hypothesis and will be subjected to formal statistical testing. Other analyses of secondary efficacy variables will be done on a hypothesis-generating basis, i.e. no p-value adjustments will be conducted, and conclusions regarding the analysis results will be commented on such a basis.

Time-to-cure

The aim of the hypothesis test is to show that the time is less among the subjects receiving PHBM 0.08% monotherapy compared to the comparator. Patients will either be classified as Cured at some point of time while in the study or leave the study without being classified as Cured. As a secondary efficacy variable, timeto-cure (clinical resolution) will be analysed. The Cox Proportional Hazards regression (subject to validity of the 'proportional hazards' assumption) and Kaplan-Meier survival plots. If the proportional hazard assumption is not fulfilled a logrank test will be performed. Not all patients may have information regarding when they were cured, e.g. due to death before being cured, or completed the study without being cured. Both the Cox Proportional Hazards regression and the Kaplan-Meier plot uses the censoring timepoint in their calculations. The censoring timepoint will be defined based on the timepoint of the last observation when cure status was assessed. The null hypothesis is that the two treatment arms have equal hazard functions. Relevant data will be presented at the Clean file meeting for discussion and acceptance.

BCVA

The VAMS states that: "Depending on the problem, this notation can be most useful when analysing or graphically plotting visual acuity scores because equal linear steps on the LogMAR scale represent equal ratios in the standard size sequence." Hence, BCVA will be presented and analysed using LogMAR values, where

$$LogMAR = \log \left(\frac{ORRES_{BCA2}}{ORRES_{BCA1}} \right),$$

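### Time-to-cure censors known treatment failures at trial exit, so its curve overstates cure and its hazard ratio depends on when each arm's failures leave

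*SAP*

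**What the plan says.** Protocol 2.3 states as a secondary hypothesis: "That time to a cure is shorter in subjects receiving PHMB 0.08% monotherapy compared to the comparator". SAP 7.9.3 gives it formal status: "Time-to-cure comparison between the treatment groups is specified as efficacy hypothesis and will be subjected to formal statistical testing". The methods are Cox regression and Kaplan-Meier plots, with a logrank test if hazards are not proportional. The null is equal hazard functions. No competing-risk method is planned.

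Under SAP 8.3, for subjects who complete or withdraw uncured, "without experiencing clinical resolution, the time to event will be right-censored at the date of completion/withdrawal". SAP 7.9.3 gives a different date, but still censors: "The censoring timepoint will be defined based on the timepoint of the last observation when cure status was assessed". Neither section separates treatment failure from loss to follow-up.

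The protocol makes failure a terminal exit. Section 5.3.2, Box X: "Alternatively, if continued deterioration occurs, cases move to Box XVIII - TREATMENT FAILURE and EXIT Trial". Section 5.3.3, on relapse: "If CULTURES are POSITIVE patients have TREATMENT FAILURE and managed as described in XIV and XVII below". Scleritis unresponsive to treatment (Box XV) also exits. The footnotes to the Schedule of Assessments end the study for a failure on the day of unmasking.

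The primary analysis (SAP 7.9.1) treats the same people differently: "Discontinued subjects will be regarded as not cured".

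**The concern.** A subject who leaves as a treatment failure is not someone whose cure status is unknown. Follow-up on the assigned treatment has ended, the allocation is opened, and 0.08% PHMB may be supplied on request (Protocol 5.3.3, Box XVII). Cure on the assigned arm can no longer be observed, and the exit happened because the subject was responding badly. Censoring there removes the worst responders from the risk set.

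Two things are at stake. The Kaplan-Meier curve, read as a probability of cure, will not agree with CRR_12 from the same trial. And the only secondary efficacy comparison tested formally will depend on how early each arm's failures exit, as well as on cure. Early failures in the test arm can make that arm look as fast as, or faster than, an arm that cures more people. With a better test arm, early failures in both arms, or mainly in the control arm, can hide a real advantage. Settling on one censoring date would not remove this.

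**Working it through.** **The plan's own figure.** The documents give no event count, hazard ratio or power for time-to-cure. The only size figure is 130 subjects, which reproduces with unpooled variance: n per arm = (1.645 + 0.842)² × (0.63×0.37 + 0.83×0.17) / 0.20² = 57.8, so 58 (116 evaluable). Then 58/0.9 = 64.4, so 65 per arm and 130 in total. This is for the primary endpoint and is not affected; it supplies the 65 per arm used below.

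**Inputs from the documents.** Control CRR_12 63% and a difference of 0.20 (Protocol 7.6); horizon Day 365 (Protocol 5.3.1, Box IV); censoring at exit (SAP 8.3). **Assumed**, because the documents are silent: the distributions of cure times and exit times.

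**Step 1, by hand.** If F of N subjects exit as failures before any cure, C are cured and the rest are followed to Day 365, then CRR = C/N but 1-KM = C/(N-F).

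| Arm | N | F | C | CRR | 1-KM |
|---|---|---|---|---|---|
| Control | 65 | 5 | 41 | 41/65 = 63.1% | 41/60 = 68.3% |
| Test | 65 | 20 | 31 | 31/65 = 47.7% | 31/45 = 68.9% |

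A cure rate lower by 10/65 = 15.4 points appears as an equal curve.

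**Step 2, closed form.** Take constant monthly hazards λ (cure) and μ (early failure). The share cured is λ/(λ+μ) × (1 - exp(-12(λ+μ))), while 1-KM is 1 - exp(-12λ). For a control arm with 63% cured and 10% early failures, λ+μ = -ln(0.27)/12 = 0.109 and λ = (0.63/0.73) × 0.109 = 0.094, so 1-KM is 67.7%. Give the test arm the same λ but more early failures. With 20% it cures 58.1%; with 30% it cures 53.0%. The cause-specific hazard ratio stays 1.00 and 1-KM stays 67.7% in both arms. With failures held uncured to Day 365 the hazard ratio is about 0.91 and 0.80.

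**Step 3, simulation.** 65 per arm, cure times uniform over Days 45-335 in both arms. Rejection rates are for the time-to-cure test alone at two-sided 5%.

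| Scenario | As written | Failures held to Day 365 |
|---|---|---|
| CRR 83% v 63%, all failures exit Days 30-120 | HR about 1.02, power about 5% | HR about 1.63, power about 69% (66% to 69% across runs) |
| Same CRR, one third exit early, rest at Day 365 | power about 52% | power about 67% |
| Same CRR, all exit at Day 365 | no difference | no difference |
| CRR 63% in both, exits Days 30-120 v 120-365 | HR about 1.9, rejection about 79% | HR about 1.0, rejection about 5% |
| CRR 63% in both, half exit early as above, rest at Day 365 | rejection about 13% | not tabulated |

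**Step 4, the SAP's decision rule.** SAP 7.1.7 declares time-to-resolution significant only if its p-value plus the primary p-value is below the overall level. That sum cannot be below α unless the primary p-value is, so with equal CRR_12 the chance of a formal claim cannot exceed about α. In the fourth scenario, the 79% becomes about 3% at 0.05 or 8% at 0.10.

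**Step 5, slow responders.** With 59 per arm, the same underlying cure times in both arms and 38% slow responders, let the test arm exit its slow responders early. It cures 55% v 66%, yet the hazard ratio as written is 1.35 in its favour; held to Day 365 it is 0.79. A milder version (60.5% v 66%) gives 1.17 and 0.89. In the stronger version the time-to-cure test alone finds the test arm significantly faster in 25% of trials. Under the sum-of-p rule at 0.05 this falls to 0.4%, about the null rate of 0.6%. It rises to 6-11% only in more extreme cases (about 80% v 60-64% cured), because the p-values are two-sided and a primary result against the test arm also satisfies the rule.

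**The case against.** **The Cox model is not invalid.** A reader might infer that censoring failures assumes they would have been cured at the same rate as those remaining. For the Cox and logrank comparison no such assumption is needed: censoring a competing event gives a valid cause-specific hazard ratio, and SAP 7.9.3 states its null in terms of hazards. This stands. The assumption enters when 1-KM is read as a probability of cure, and the cause-specific ratio alone does not answer the hypothesis as worded for all treated subjects.

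**A large formal false-positive rate.** A reader might take the 79% as the planned test's type I error. It is not. The sum-of-p rule cuts it to about 3% or 8%, and the primary analysis would still show any shortfall in cure rate. The rule does not correct the reported hazard ratio or curve, and it cannot restore power.

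**The scenarios are extreme.** Fair. The protocol has late exit routes (relapse after Day 335, ongoing inflammation at Day 365), re-treats culture-negative relapses, calls culture very insensitive, and describes progression over weeks and months. The effect shrinks as exits move later and vanishes at Day 365. It also largely cancels where the arms' failure hazards are equal: one such case gave hazard ratios of 0.78 and 0.79 under the two approaches.

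**The gain in power is not a gain about speed.** Also fair. In the 83% v 63% scenario, cured subjects in both arms are cured at the same pace, so the hazard ratio of 1.63 comes from the difference in cure rate, which CRR_12 already tests.

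**Conclusion.** The concern holds as a matter of estimand and reporting. Known failures are censored in one analysis and counted as not cured in the other. 1-KM will therefore overstate cure and disagree with CRR_12 whenever failures exit before later cures, and the hazard ratio depends on exit timing that the plan does not control.

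The size rests on assumed exit times. For CRR_12 of 83% v 63%, power at two-sided 5% runs from about 5% (all failures out by Day 120) through about 52% (one third out early) to no loss (all at Day 365), against 67-69% with failures held. For equal CRR_12, the hazard ratio can reach about 1.9.

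The documents do not support a claim of large formal type I error, nor that the Cox model is invalid. The harm is a misleading hazard ratio and curve, and lost power, on a formally tested secondary hypothesis. The primary analysis and the sample size are untouched.

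**What to change.** In SAP 7.9.3 and 8.3:

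- Keep in the risk set, uncured to Day 365, every subject whom the primary rule counts as not cured because of treatment failure or discontinuation for disease or treatment reasons. Name ocular intolerance and adverse events explicitly. Both are listed in Protocol 4.4, and dose-limiting events occurred in 3/27 = 11.1% of the 0.08% group in Phase 1, so leaving them out could matter.
- Censor, at the last cure-status assessment, only loss or withdrawal unrelated to disease or treatment. This departs from the primary rule, which counts every discontinuation as not cured, and the SAP should say so. It also settles the two conflicting censoring dates.
- Replace the Kaplan-Meier plot with cumulative incidence of cure, with treatment failure as the competing event.
- Report the planned cause-specific Cox model as supportive.

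The cost is SAP wording and a small programming change. No new data are needed, because reasons for discontinuation are already recorded. Protocol 7.4.1 names Cox regression and Kaplan-Meier plots, so if the change is judged to touch a principal feature, the SAP's own introduction calls for a protocol amendment. One downside must be stated when reporting: the new hazard ratio reflects both the chance and the speed of cure, and so overlaps with CRR_12.

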8.4 Compliance

The rate of compliance will be assessed using the Yes / No answer to the eCRF question: Was the study drug administration compliant with the protocol?

8.5 Duration

The time to resolution in days will be computed as the time in days from randomisation to the day of resolution plus 1 day.

9 References

- 1. ICH Harmonised Tripartite Guideline for Statistical Principles for Clinical Trials E9. February 1998.
- 2. ICH Harmonised Tripartite Guideline for Structure and Content of Clinical Trial Reports E3. November 1995.
- 3. Visual acuity measured standard. International Council of Ophthalmolgy, Italian Journal of Ophthalmology II / I 1988, pp 1 / 15.

10 Signoff

We have read this SAP for the 043-SI study and confirm that, to the best of our knowledge, the statistical analyses to be performed in this study are accurately described.

SIFI SpA Approver: [name] MD Ph.D., Medical Affairs Manager SIGNATURE AND DATE

LINK Medical SAP Author: [name], Sr. Statistician

SIGNATURE AND DATE

LINK Medical SAP Approver: [name], Associate Director Biostatistics

[name]

SIGNATURE AND DATE

Verification

Transaction 09222115557449620377

Document

Odak-sifi_43-

si_statisticalanalysisplan_v3.0_jul_01_2021_clean

Main document

26 pages

Initiated on 2021-07-01 14:42:19 CEST (+0200) by Intility

eSign (le.

Finalised on 2021-07-02 10:29:44 CEST (+0200)

Initiator

Intility eSign (Ie)

[contact]

Signing parties

[name] (CE)

On behalf of Link Medical Research [contact] [name]

[name]

Signed 2021-07-01 14:42:42 CEST (+0200)

[name] (MS)

On behalf of LINK Medical Research AB [contact] [name]

[name]

Signed 2021-07-02 10:29:44 CEST (+0200)

[name] (VP)

[contact]

Hope

Signed 2021-07-02 09:44:50 CEST (+0200)

This verification was issued by Scrive. Information in italics has been safely verified by Scrive. For more information/evidence about this document see the concealed attachments. Use a PDF-reader such as Adobe Reader that can show concealed attachments to view the attachments. Please observe that if the document is printed, the integrity of such printed copy cannot be verified as per the below and that a basic print-out lacks the contents of the concealed attachments. The digital signature (electronic seal) ensures that the integrity of this document, including the concealed attachments, can be proven mathematically and independently of Scrive. For your convenience Scrive also provides a service that

Verification

Transaction 09222115557449620377

enables you to automatically verify the document's integrity at: https://scrive.com/verify
